12. The subject has reported previously participating in an investigational study involving LNPs.
13. The subject has a history of hypersensitivity or serious reactions (eg, anaphylaxis, urticaria, other significant reaction) to previous vaccinations.
14. The subject has any known or suspected autoimmune disease or immunosuppressive condition, acquired or congenital, as determined by medical history and/or physical examination.
15. The subject has a history of inflammatory arthritis.
16. The subject has a neurologic disorder (eg, history of seizures, Guillain-Barré syndrome, dementia, vasculitis, or any known congenital or acquired disorder).
17. The subject has a history of febrile disease with arthritis or arthralgia within 2 weeks of dose administration.
18. The subject received immunoglobulins and/or any blood products within the 3 months preceding the administration of the study drug or plans to receive such products at any time during the study.
19. The subject has had chronic administration (defined as more than 14 continuous days) of an immunosuppressant or other immune-modifying drug within 6 months before vaccine administration or plans to receive any products during the active vaccination period (through 4 weeks after their last planned vaccination). An immunosuppressant dose of a glucocorticoid will be defined as a systemic dose of  $\geq 10$  mg of prednisone per day or equivalent. The use of topical, inhaled, and nasal glucocorticoids will be permitted.
20. The subject has any acute illness at the time of enrollment (defined as the presence of a moderate or severe illness with or without fever, or an oral body temperature  $>37.9^{\circ}\text{C}$  on the planned day of vaccination). In such cases, subjects may be re-evaluated during the

screening period for resolution of the illness to allow at least 3 days of wellness before the planned vaccination as long as they remain within the 28-day screening period.

21. The subject has any significant disorder of coagulation (acquired or hereditary) requiring ongoing or intermittent treatment. Subjects receiving prophylactic antiplatelet medications, eg, low dose acetylsalicylic acid ( $\leq 100$  mg/day or equivalent), and without clinically apparent bleeding tendency, are eligible.
22. The subject has a history of idiopathic urticaria.
23. The subject has a documented history of alcohol abuse or drug addiction within 1 year before the planned day of dose administration.

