### **3.3 Withdrawal of Subjects From the Study**

#### **3.3.1 Reasons for Withdrawal**

Subjects can withdraw consent and discontinue from the study at any time, for any reason, without prejudice to further treatment.

The investigator can also withdraw a subject, upon the request of Moderna Therapeutics, Inc. or if Moderna Therapeutics, Inc. terminates the study. Upon occurrence of a serious or intolerable AE, the investigator will confer with the Sponsor or designee. If a subject desires to withdraw from the study because of an AE, the investigator will try to obtain agreement to continue to follow that subject for that event only until it is resolved or until stable and then complete an EOS form. In the event of a safety concern that results in withholding from further vaccination, the subject will be continued in the trial for safety evaluations.

Every reasonable attempt will be made to follow subjects for safety throughout the entire trial period even if further vaccination is withheld or the subject misses visits. The reason for subject withdrawal or lost to follow-up will be documented.

The investigator, in consultation with the Sponsor's medical monitor, **may** withhold a subject **from further vaccination** if the subject experiences any of the following:

1. Becomes pregnant;
2. Develops, during the course of the study, symptoms or conditions listed in the exclusion criteria;

3. Experiences an AE (other than reactogenicity) after vaccination that is considered by the investigator to be possibly or probably related to treatment and is of Grade 3 (severe) or higher severity;
4. Experiences an AE or SAE that, in the judgment of the investigator, requires study drug withdrawal due to its nature, severity, or required treatment, regardless of the causal relationship to treatment;
5. Experiences a clinically significant change in clinical laboratory test results, vital signs, or general condition that, in the judgment of the investigator, requires treatment withdrawal;
6. Experiences anaphylaxis clearly attributed to study vaccine;
7. Experiences generalized urticaria related to the study vaccine.

The reason for withdrawing or refusing from further vaccination will be recorded. In addition, if a subject refused further vaccination they will be continued in the trial with all planned visits and assessments relative to the vaccination schedule and including visits through 1 year post final vaccination.

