### **3.4.2 Treatments Administered**

Dosing will begin with 10-µg mRNA-1325 or placebo (Cohort 2), followed by 25-µg mRNA-1325 or placebo (Cohort 3), and then 100-µg mRNA-1325 or placebo (Cohort 4). The rationale for dose selection is described in [Section 1.5](#). Dosing cohorts will advance as described in [Section 3.4.2.1](#).

Vaccine will be administered as an IM injection (0.5 mL) into the deltoid muscle as a 2-dose vaccination schedule at Visits 1 and 4 (at least a 28-day interval between dosing). The second dose of study drug will be administered preferably in the same arm used for the first dose.

The clinic will be appropriately staffed, trained on emergency resuscitation, and have stocked available rescue medications (such as epinephrine, steroids, antihistamines, and IV fluids) should any severe reaction (eg, anaphylaxis or profound urticaria) occur that requires immediate intervention.

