### **Safety Monitoring Committee**

The SMC will review data for dose escalation when at least 90% of subjects dosed (eg,  $\geq 27$  out of 30 subjects) in Cohort 2 (10- $\mu$ g mRNA-1325 or placebo) have safety data inclusive of their visit 7 days following the second vaccination (Visit 5). Once a recommendation is given by the SMC, the Sponsor will approve advancing to Cohort 3 (25- $\mu$ g mRNA-1325 or placebo). Cohort 4 (100- $\mu$ g mRNA-1325 or placebo) will be randomized following SMC review and Sponsor approval of Cohort 3 (data inclusive of 7 days following the second vaccination of  $\geq 90\%$  of subjects dosed [eg,  $\geq 27$  out of 30 subjects]).

To allow cohort advancement, the following data from the highest dosed cohort is expected to be reviewed by the SMC: 1) toxicity scoring of safety laboratory test results through 7 days following the second vaccination (through Visit 5); 2) toxicity scoring of vital sign measurements and reactogenicity through 7 days following the first and second vaccination (through Visit 5); 3) all unsolicited AEs (with grading and relatedness). Data will be prepared by dose category and timing relative to last vaccination. As safety data on all cohorts accumulate, the SMC will include in their review ongoing AEs as well as cumulative safety laboratory test results, reactogenicity, and AEs across vaccine doses as long as subjects remain in Part A of the study, thereby providing a cumulative review of safety. Should a cohort pause occur due to pre-specified criteria ([Section 3.4.2.2](#)), the SMC will be convened for an unscheduled (ad hoc) meeting and receive specific safety data related to the trigger of the pause.

The SMC may recommend advancement to the next dosing cohort, request additional information prior to providing a recommendation, recommend stopping the study, recommend changes to study conduct and/or the protocol, or recommend additional operational

considerations due to safety issues that arise during study conduct. The Sponsor has the authority to accept (or amend) the SMC recommendations, to stop the study at any time, to request a cohort pause for safety concerns (to be addressed by the SMC), and to request additional consultation during study conduct for either safety concerns or operational issues. The SMC will also be convened should a pause rule be triggered or at the request of the IST, the investigator(s), or the Sponsor.

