### **3.4.2.2 Pause Rules**

During the active vaccination period, if any of the following events occur and are assessed to be potentially mRNA-1325 related, the cohort will be paused for further enrollment and vaccination, and an unscheduled SMC will be convened to assess specific data concerns and make recommendations:

- Two or more Grade 3 (or greater) reactogenicity events (whether systemic or local) within a dose cohort following any single (eg, the first, the second) vaccination
- Two or more Grade 3 (or greater) same laboratory toxicity score within a dose cohort
- One or more SAEs assessed as vaccine related, including any systemic hypersensitivity reaction

An unscheduled SMC may also be convened (with vaccination pausing if deemed necessary), by the investigator, IST, or Sponsor, if any other significant safety or tolerability issues are identified in the comprehensive review of available data that warrant further evaluation before additional subjects are dosed. This may include emerging non-clinical data, clinically relevant AEs, or relevant data from other sources indicating safety concerns even if the event(s) per se does not meet the criteria specified in this section.

Should a pause be triggered in the study, then each subject's visits will continue until the next scheduled vaccination visit. Should a pause affect a subject's vaccination visit, then the window for that subject's vaccination visit will be suspended until the pause is lifted and vaccination can resume. Once the pause is lifted at the site, vaccination should be reinstated as soon as possible. Visits should thereafter be scheduled as if they had received their second vaccination within the 28 (+7) day time window.

Should a pause be prolonged such that the second vaccination takes place outside the 28 (+7) day time window, the Sponsor has the option to add additional subjects in a dosing cohort to achieve the original number of subjects planned to be dosed within the 28 (+7) day time window. If a subject is in the screening period for more than 28 days as the result of a pause, they may be rescreened for study eligibility as long as they continue to provide consent to participate in the study.

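### Section 3.3.1 leaves withholding of the second dose to discretion after vaccine-attributed anaphylaxis or vaccine-related generalized urticaria, and no other text bars that dose for the subject concerned

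*Protocol*

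**What the plan says.** Section 3.3.1 of the protocol governs individual decisions on the second dose. One permissive verb, which the protocol prints in bold, covers all seven listed events. Four of them bear on this point:

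- Item 2: "Develops, during the course of the study, symptoms or conditions listed in the exclusion criteria".
- Item 3, an adverse event other than reactogenicity that is considered "possibly or probably related to treatment and is of Grade 3 (severe) or higher severity".
- Item 6: "Experiences anaphylaxis clearly attributed to study vaccine".
- Item 7: "Experiences generalized urticaria related to the study vaccine".

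The same section obliges the investigator to confer with the sponsor after a serious or intolerable adverse event. It also keeps a subject whose vaccination is withheld for safety in the trial for safety evaluations.

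At entry the rule is stricter. Exclusion criterion 13 in Section 3.2.2 turns a person away on this ground: "The subject has a history of hypersensitivity or serious reactions (eg, anaphylaxis, urticaria, other significant reaction) to previous vaccinations". The protocol also foresees such reactions on study, because Section 3.4.2 requires rescue medication on site "should any severe reaction (eg, anaphylaxis or profound urticaria) occur that requires immediate intervention".

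**The concern.** Section 1.4 describes the trial as first-in-human. It gives two doses to healthy adults, and Section 1.2.4 describes two of the lipids in the formulation as novel and absent from FDA-approved products. A subject who has had an anaphylactic reaction put down to the first injection has nothing to gain from the second that would justify leaving the decision open.

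The result is also uneven. A volunteer who once reacted this way to a different vaccine cannot enter. A volunteer who reacts this way to the study vaccine itself may, on the words of Section 3.3.1, be given it again without breaching that section. What is at stake is the safety of that one subject. The analysis is not affected.

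**Working it through.** No formula applies and the protocol states no figure to reproduce. The check is whether any text outside the list in Section 3.3.1 makes withholding mandatory for the individual who reacted.

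1. **Exclusion criterion 13 (Section 3.2.2).** This is an entry criterion about earlier vaccinations. Nothing says it is applied again before dose 2. Once a subject is enrolled, it returns only through item 2 of Section 3.3.1, which is discretionary as well.
2. **Item 3 of Section 3.3.1.** The same reaction may also qualify as a related event of Grade 3 or higher. That leads back to the same optional verb.
3. **Serious adverse events (Section 3.3.1).** The duty is to confer with the sponsor, which is consultation and not a bar.
4. **Pause rules (Section 3.4.2.2).** One vaccine-related serious adverse event, including a systemic hypersensitivity reaction, is enough to trigger them, and then "the cohort will be paused for further enrollment and vaccination". The affected subject is in that cohort, so dosing stops for that subject too while the pause lasts. Once it is lifted, vaccination is to restart promptly, and no exception is made for the subject who reacted.
5. **Safety Monitoring Committee (Section 3.4.2.1).** Its options include changes to study conduct or to the protocol and further operational measures. These are broad enough for it to advise against a second dose for one person. They remain advice: "The Sponsor has the authority to accept (or amend) the SMC recommendations".
6. **Day-of-vaccination stop (Table 6-1, footnote m).** This is a true bar, but it covers only vital signs of Grade 2 or higher and intercurrent illness, including fever.

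Of these six texts, none makes withholding mandatory for the individual beyond the length of a pause.

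Two comparisons show that the protocol does use hard stops where it wants them. Under Table 6-3 a systolic pressure of 151 mm Hg is Grade 2, so footnote m forbids vaccination that day. Pregnancy, item 1 of the same discretionary list, is backed by exclusion criterion 3 (positive test on the day of vaccination), by the negative test required before dosing in Section 3.2.3.2, and by the test before each dose in Table 6-1, footnote k. Items 6 and 7 have no such backing.

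**Extent.** Items affected: 2 of 7. Planned mRNA-1325 recipients to whom the rule applies: 24 per cohort x 3 cohorts = 72. This is a count of people covered by the rule and not an expected number of events.

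**The case against.** The strongest reply is that *may* grants authority and does not invite re-dosing. Items 4 and 5 support this. They sit under the same verb, yet describe events that the investigator has already judged to require withdrawal of treatment. Read as purely optional, the clause would let the investigator decline what he or she has just found necessary, so the list is more sensibly read as saying when the investigator is empowered to stop. This reading is fair, and the wording is ambiguous to that extent. But a power to withhold is still not a duty to do so, and under either reading no duty is stated.

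The second reply is that mandatory layers already exist: the cohort pause, the unscheduled SMC meeting, and the consultation with the sponsor and medical monitor. This stands as to likelihood. A second dose would require the pause to be lifted after review and the investigator then to choose to give it. It does not stand as a subject-level bar, for the reasons in steps 3 to 5.

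The third reply is that generalized urticaria carries no severity threshold in item 7, so mild cases could properly be left to judgment. There is something in this, and it is the main discretion that would be lost. It is weak as a defence of the present text, because exclusion criterion 13 names urticaria next to anaphylaxis with no separate severity threshold for it.

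A reader might infer that the protocol directs a second dose after anaphylaxis, or that Section 3.3.1 contradicts exclusion criterion 13. The documents support neither. No text calls for re-dosing, and an entry criterion can differ from an on-study rule without contradiction. A reader might also extend the point to pregnancy, but that is already covered by the three provisions named above.

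**Conclusion.** The point holds as a rule that is too lax in a subject-safety matter. Section 3.3.1 leaves withholding optional for two events where attribution to the vaccine is already part of the definition, and nothing elsewhere closes the gap for the individual. Its practical weight is limited, because the existing oversight makes re-dosing unlikely. It is a cheap improvement worth making.

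It would be tempting to attach a probability of harm. The documents give no rate for these reactions and none for re-dosing after one, so any such figure would rest on assumption alone, and none is offered. No sample size, endpoint or analysis changes.

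The conclusion rests on the protocol text alone.

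**What to change.** In Section 3.3.1, take items 6 and 7 out of the discretionary list and state that further vaccination must be withheld after either event, with the subject remaining in safety follow-up as that section already provides. In Section 3.4.2.2, add one clause saying that lifting a pause does not permit re-dosing such a subject. The other items can stay discretionary. No change is needed for pregnancy, and no rule of precedence over items 2 to 5 is needed once items 6 and 7 are mandatory.

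The cost is wording in two sections, a slight loss of investigator discretion (mainly for mild urticaria), and an occasional subject without dose 2. Per event, that is at most 1 of the 24 active subjects in a dose group missing from the Per-Protocol data. This measures the price of the change and not the harm in the present text. The subject stays in the Safety set, which requires only one dose.

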### **3.3.2 Handling of Withdrawals**

When a subject withdraws from the study, the reason(s) for withdrawal will be recorded by the investigator on the relevant page of the eCRF. These subjects will also be requested to complete all Visit 7 assessments. Any subject who fails to return for final assessments will be contacted by the site with a minimum of 3 phone call attempts, followed by a certified letter. After this final attempt the subject will be declared “lost to follow-up” on the EOS.

Lost to follow-up is defined by the inability to reach the subject after a minimum of 3 documented phone calls, faxes, text messages, or emails as well as lack of response by subject to 1 registered mail letter. All attempts should be documented in the subject’s source documents.

### **3.3.3 Replacements**

Any subject who is withdrawn, who is significantly outside the allowed vaccination window, or is lost to follow-up from the study will not be replaced without the prior authorization of the Sponsor.

## **3.4 Study Treatments**

### **3.4.1 Method of Assigning Subjects to Treatment Groups**

Subjects will be randomly assigned to a cohort after all entry criteria have been satisfied on Visit 1. A randomization table will be pre-generated, and only the unblinded pharmacy personnel will have controlled access. Subjects will be randomly assigned in a blinded fashion in an approximate 4:1 ratio to mRNA-1325 or placebo at 1 of 3 dose levels (10 µg, 25 µg, or 100 µg). The first 3 subjects for each dose level will be randomized to mRNA-1325. Approximately two-thirds of the enrolled subjects at each dose level will be flavivirus naïve and approximately one-third will be flavivirus seropositive as a result of having received a yellow fever vaccination in the past 20 years.

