## 1.4 Rationale for Study

No vaccines have yet been licensed for prophylaxis of ZikaV infection. Of the approaches currently in development, the VLP and live attenuated vaccines ([Akahata et al 2010](#); [Darwin et al 2011](#); [Wang et al 2008](#); [Brandler et al 2013](#)) show the greatest pre-clinical potential. However, both are expected to be more complex, costly, and longer to develop and scale-up than mRNA due to the need to establish, optimize, and characterize vaccine specific growth substrates, formulations, and dedicated production facilities. In addition, live attenuated vaccines, such as yellow fever vaccines, pose the risk of recombination with circulating wild type flaviviruses, reversion to pathogenicity, and vaccine-virus associated disease, particularly in immunocompromised populations. The Sponsor believes that on the basis of pre-clinical data with this and other vaccines in the Moderna Therapeutics, Inc. development pipeline, mRNA-1325 has the potential to achieve at least equivalent and more predictable levels of efficacy and safety, with more rapid and reliably scalable manufacturing.

The purpose of this Phase 1, first-in-human, randomized, placebo-controlled, dose-ranging, study is to evaluate the safety and immunogenicity of mRNA-1325 in healthy adult subjects in a non-endemic region. The primary objective of this study is to assess the safety profile of mRNA-1325 compared with placebo. The study will also evaluate immunogenicity by assessing changes from Baseline in ZikaV-specific neutralizing antibody titers. The safety profile and immune response(s) will be compared between flavivirus-seropositive and flavivirus-seronegative subjects to indicate the ability of the selected dose to safely protect populations in both endemic and non-endemic regions.

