## **2 Study Objectives**

### **2.1 Primary Objective**

The primary objective of this study is to assess the safety of a 2-dose vaccination schedule of mRNA-1325 Zika vaccine, given 28 days apart, across a range of dose levels in flavivirus-seronegative and flavivirus-seropositive subjects compared with placebo.

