**Figure 3-1 Cohort and Treatment Assignment**

[figure not shown]
Cohort	Flavivirus Status	Treatment Assignment (µg mRNA-1325 or placebo)	Total (Ratio)
2	+	10	30 (4:1)
	-	10	
	+	placebo	
	-	placebo	
3	+	25	30 (4:1)
	-	25	
	+	placebo	
	-	placebo	
4	+	100	30 (4:1)
	-	100	
	+	placebo	
	-	placebo	

Abbreviations: +, flavivirus seropositive; -, flavivirus seronegative.

For each cohort, a sentinel safety group will occur with 3 flavivirus-seronegative subjects randomized to mRNA-1325 and followed for 7 days after first vaccination, with review of reactogenicity and safety laboratory results, prior to randomizing the remainder of the cohort. An IST will oversee the safety of the trial and will review blinded safety data during Part A of the study to ensure adherence to the protocol, monitor safety laboratory test results and reactogenicity, and raise concerns to the SMC should there be safety issues or operational challenges that could affect subject safety. Only after review by the IST of the blinded safety data (reactogenicity, safety labs, and AEs) through 7 days following first vaccination of the sentinel safety lead-in for each cohort planned will approval be given to allow randomization of the remainder of that cohort. The SMC will approve escalation to the next higher dosing cohort after review of blinded safety data of the currently dosed cohort through 7 days following the second vaccination and any cumulative safety data of all cohorts as the trial advances. The SMC will also be convened (ad hoc meeting) if a pause rule is triggered.

A diagram of the dosing schema by cohort is shown in [Figure 3-2](#).

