**Figure 3-2 Dosing Schema by Cohort**

Abbreviations: D, day; Plc, placebo; SMC, safety monitoring committee.

Note: Yellow shading depicts safety follow-up of the first vaccination period and grey shading depicts safety follow-up of the second vaccination period for cohorts by dose sequence.

Note: The SMC will approve escalation to the next higher dosing cohort after review of blinded safety data of the currently dosed cohort through 7 days following the second vaccination and any cumulative safety data of all cohorts as the trial advances.

The vaccine will be administered as an IM injection (0.5 mL) into the deltoid muscle as a 2-dose vaccination schedule at Visits 1 and 4 (at least a 28-day interval between dosing). The second dose of study drug will be administered preferably in the same arm used for the first dose. Vaccine accountability, dose preparation, and vaccine administration will be performed by unblinded pharmacy personnel, who will not participate in any other aspect of the study. The remainder of the site staff and all subjects will remain blinded to treatment assignment.

Screening and consent will occur over a 28-day period before randomization (West Nile virus serology screen can occur up to 90 days prior to randomization). A total of 30 subjects for each dose cohort will be assigned, 24 subjects to mRNA-1325 and 6 subjects to placebo (approximate 4:1 ratio overall). The first 3 subjects for each dose level will be randomized to mRNA-1325. Subjects who meet all eligibility criteria will receive the first vaccination at Visit 1. Of note, a subject who has met all eligibility criteria but is noted to have a blood pressure, heart rate or respiratory rate that is Grade 2 or greater (even after relaxing/resting) in the clinic on the day of vaccination should not receive a vaccination on that day and will need to return on a subsequent day for their vaccination. Similarly, if a subject has a fever ( $>37.9^{\circ}\text{C}$ ) or an intercurrent illness, vaccination should be withheld until resolved (as specified in exclusion criterion 20). Each subject will be monitored in the clinic for at least 1 hour following vaccination to assess for immediate reactogenicity, with vital sign measurements and local and

systemic reactogenicity toxicity scored at that time. The highest toxicity recording will be entered into the electronic case report form (eCRF).

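### Section 3.4.1 sets the 4:1 ratio and the serostatus mix per dose cohort only and makes no provision for allocating by flavivirus serostatus

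*Protocol*

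**What the plan says.** Section 3.4.1 gives the assignment method in a few sentences. On the list: "A randomization table will be pre-generated, and only the unblinded pharmacy personnel will have controlled access". On the ratio: "Subjects will be randomly assigned in a blinded fashion in an approximate 4:1 ratio to mRNA-1325 or placebo at 1 of 3 dose levels". On the mix, stated for those enrolled at each dose level and not for each arm: "approximately one-third will be flavivirus seropositive", with the other two-thirds naïve. On the first assignments: "The first 3 subjects for each dose level will be randomized to mRNA-1325".

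Section 3.1 adds the counts ("A total of 30 subjects for each dose cohort will be assigned, 24 subjects to mRNA-1325 and 6 subjects to placebo") and the sentinels' serostatus: "a sentinel safety group will occur with 3 flavivirus-seronegative subjects randomized to mRNA-1325". The table under Figure 3-1 lists four cells per cohort, serostatus by treatment, but gives a number only for the cohort total of 30.

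Section 2.1 sets the primary objective as safety "across a range of dose levels in flavivirus-seronegative and flavivirus-seropositive subjects compared with placebo". Section 1.4 adds: "The safety profile and immune response(s) will be compared between flavivirus-seropositive and flavivirus-seronegative subjects".

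Sections 3.6.5 and 3.6.5.2 pool placebo subjects across cohorts. Section 3.6.7 locks and analyses the data as each cohort completes Part A, with later locks cumulative and reported by cohort as well as in aggregate.

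**The concern.** Serostatus is known at screening, defines two groups named in the primary objective, and could plausibly affect both reactogenicity and Zika titers. It is the obvious factor on which to control allocation, and the section on allocation does not use it.

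Two consequences follow if the method is carried out as written.

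- **A systematic tilt.** Three seronegative subjects per cohort go to vaccine by rule. The remaining pool is therefore richer in seropositive subjects than the whole cohort, and all placebo subjects come from that pool. The placebo arm is expected to be more seropositive than the vaccine arm.
- **Chance in a small cell.** With six placebo subjects per cohort, the number who are seropositive is left to chance. A cohort could reach its data lock with one or none.

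**Working it through.** **The plan's own figures.** 30 × 4/5 = 24 vaccine and 30 × 1/5 = 6 placebo per cohort; 3 × 30 = 90 in total. These reproduce. Section 3.6.3 says no formal sample size calculation was made, so there is no power figure to check.

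**Inputs.** Per cohort: 30 subjects, 24 vaccine and 6 placebo (section 3.1); about one-third seropositive, so 30/3 = 10 (section 3.4.1); 3 seronegative sentinels on vaccine (section 3.1). That leaves 27 subjects, 10 of them seropositive, for 21 vaccine and 6 placebo places. Two assumptions are mine: the 27 are allocated without regard to serostatus, and the seropositive count is 10, with 9 to 11 shown as a range.

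**Expected tilt.** Seropositive subjects on placebo: 10 × 6/27 = 2.22, or 2.22/6 = 37%. On vaccine: 10 − 2.22 = 7.78, or 7.78/24 = 32%. The gap is 4.6 percentage points.

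**Chance variation per cohort.** The seropositive placebo count is hypergeometric (27 subjects, 10 seropositive, 6 drawn):

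- P(0) = C(17,6)/C(27,6) = 12,376/296,010 = 4.2%
- P(1) = 10 × C(17,5)/C(27,6) = 61,880/296,010 = 20.9%
- P(at most 1) = 25.1%

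Over three cohorts, the chance that at least one has none is 1 − (1 − 0.0418)³ = 12%. The chance that at least one has at most one is 1 − (1 − 0.251)³ = 58%.

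**Pooled placebo group (18 subjects).** Mean 3 × 2.22 = 6.7. Variance per cohort = 6 × (10/27) × (17/27) × (21/26) = 1.13, so the pooled SD = √(3 × 1.13) = 1.8. Convolving the three cohorts gives P(3 or fewer) = 3.8% and a central 95% range of about 3 to 10.

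**Sensitivity to the seropositive count.**

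| Seropositive per cohort | P(0) in a cohort | P(at most 1) in a cohort | Pooled mean | P(pooled 3 or fewer) |
|---|---|---|---|---|
| 9 | 6.3% | 32% | 6.0 | 7.7% |
| 10 | 4.2% | 25% | 6.7 | 3.8% |
| 11 | 2.7% | 19% | 7.3 | 1.7% |

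**With stratification.** Seropositive 8 vaccine and 2 placebo; seronegative 3 sentinels plus 13 vaccine and 4 placebo. Totals: 8 + 3 + 13 = 24 and 2 + 4 = 6. The seropositive share is 8/24 = 33% on vaccine and 2/6 = 33% on placebo, so the tilt is gone.

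**What stratification does not do.** Six seropositive placebo subjects remain few: with no events in 6, the two-sided exact 95% upper limit is 1 − 0.025^(1/6) = 46%.

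**The case against.** **Silence is not a statement.** A reader might infer that the protocol prescribes one unstratified list per dose level. It does not say so. It mentions a pre-generated table and leaves its structure open. The four cells under Figure 3-1, and an inclusion criterion that speaks of subjects assigned to the seropositive group, fit a stratified list without establishing one. The drawings for Figures 3-1 and 3-2 were not in the copy read, and a separate randomization specification may settle the matter. This stands, and it makes every probability above conditional. It does not dispose of the point: section 3.4.1 is where the protocol sets its allocation method, and it ties ratio and mix to the cohort only.

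**Placebo is pooled.** A reader might infer that the seropositive comparison rests on about two controls, or almost none. The documents do not support that for the final analysis, where each dose level is set against all placebo recipients and the seropositive part averages about 6.7. This stands. The per-cohort figures bear on the interim analyses: at the first lock only Cohort 2's six placebo subjects exist. Section 1.5 shows that a group-unblinded immunogenicity analysis of Cohort 2, reported for both serostatus groups, informed a later design decision.

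**The bias is small.** A reader might infer that the pooled vaccine-placebo difference is seriously confounded. If an event rate differed by 30 points between serostatus groups (an assumption; the documents give no figure), the expected distortion would be 0.046 × 30 = 1.4 points, in a descriptive analysis. Immunogenicity is judged on change from Baseline, and the comparison in section 1.4 is between serostatus groups, so neither depends heavily on placebo balance. This stands too.

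**The real limit is sample size**, which section 3.6.3 attributes to feasibility. Stratifying fixes about 6 seropositive controls where about 6.7 would be expected without it. The gain is control over balance, not precision.

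**Conclusion.** The point holds in a limited form. The protocol fixes ratio and mix per cohort and does not provide for allocation by serostatus, while naming both serostatus groups in its primary objective and forcing three seronegative subjects per cohort onto vaccine. Followed as written, this gives an expected 37% against 32% seropositive (placebo against vaccine), a 4.2% chance of no seropositive placebo subject in a cohort and a 25% chance of at most one. The effect on the final pooled comparison is modest; the main exposure is at the cohort-by-cohort locks.

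These figures assume allocation blind to serostatus among the 27 non-sentinel subjects, exactly 6 placebo per cohort, and about 10 seropositive subjects per cohort.

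Nor can an overall split of 6 seropositive and 12 seronegative placebo subjects be promised. Section 1.5 shows that Cohort 2 has already been enrolled and analysed, so its split is fixed.

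**What to change.** For each cohort not yet randomized, state in section 3.4.1 that the list is stratified by flavivirus serostatus within the cohort, and give target counts:

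- seronegative: 3 sentinels on vaccine, then about 13 vaccine to 4 placebo;
- seropositive: about 8 vaccine to 2 placebo.

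This keeps about 24:6. The counts are targets because the mix is only approximate. With 9 or 11 seropositive subjects, placebo can stay at 2 and 4 while vaccine takes up the difference: 7 seropositive and 17 seronegative, or 9 and 15, each totalling 24 with sentinels included.

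Add the cell counts to Figure 3-1, and state that vaccine-placebo differences will also be summarised by serostatus. If the list is already stratified, one sentence and the cell counts are enough.

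The cost is a revised list specification and a short text change, with no extra subjects or visits. It removes the tilt and the chance imbalance in the cohorts it reaches. Cohort 2 stays as randomized.
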